CTEPH is an acquired pulmonary hypertension disease with poor prognosis, 5-year mortality rate of the patients without any intervention can be as high as 90%[1]. It is generally believed that pulmonary thrombosis in these patients can be attributed to residual unresolved thrombus in acute pulmonary embolism patients or to the deep vein thrombus in lower extremities[2, 3]. 12000 to 15000 new cases of CTEPH was found every year in the United States[4], for these patients, PEA surgeries was reported as a golden standard therapy with a significantly better survival prognosis and life quality achieved compared with pure medicine therapy or pulmonary balloon angioplasty by many centers[5-7]. However, even in the United States, only 300 cases can received PEA therapies each year, the reasons for this low population received PEA surgeries are as below: 1). PEA is a extremely skill-demanding operation for the cardiac surgeons, it is reported that 1/2 to 1/3 of CTEPH patients are considered inoperable by surgeons in Europe[7]. Half of the reasons considered inoperable was the embolism location considered difficult to be found and removed during the operation[7]; Therefore, accurate positioning and complete removal of the embolism for patients with CTEPH are the key to successful operation. The latest 3-D imaging technology can accurately assess the obstructive severity of each pulmonary segments, Rotating 3-D pulmonary angiography can analyze the location and direction of each pulmonary artery, which can help the surgeons to determine the surgical difficulty of each pulmonary segment for each patient. In summary, PEA surgeries guided with high-definition 3-D imaging techniques might lead to a better hemodynamic result better survival result in the long-term period after surgeries, and might provide a solution to position the embolism before surgeries, so as to more conveniently remove the pulmonary embolism during the surgeries.

2 Objectives(Focus of the study)

- 1) To investigate the importance of the appliance of the 3-D imaging technique for PEA surgeries,especially for patients with peripheral UCSD levels;
- 2) To establish a standard assessing method with high-definition enhanced CT scanning and pulmonary angiography;establish a quantitative scoring method using CT scanning and pulmonary angiography to assess the severity of CTEPH and surgical indications;

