① According to the imaging examinations before surgeries, the location of each occluded pulmonary segment and their shape were identified and the affected pulmonary segments were divided into 3 types: i) segments that are easy to reach; ii) segments that are hard to reach (seen in the picture below), and severely occluded; iii) segments that are hard to reach but slightly occluded;

[figure not shown]
An example of segments hard to reach. As shown in the picture, the shape of LA5 of this patient is exactly perpendicular to the surgical direction, which lead to a fact that the embolism in this segment very hard to strip. For the subsegment LA8a+b, it is too far away from the proximal artery, which is very hard to reach at surgeries.

② All the occlusion severity of each segment and narrow severity of each segment is assessed with CT scanning;

An example of constructed CT imaging of the pulmonary segment: A demonstration of the anatomic structure of pulmonary segments. White arrow: not severely narrow segment of RA9; Red arrow: severely narrow segment of LA4.

4) Research process:seen in the picture below.

4 Eligibility/intervention information/Arm information

Eligibility:

Patients were **eligible** if they had met all the following conditions:

[figure not shown]
- 1) Diagnosed with CTEPH by pulmonary angiography and RHC examinations;
- 2) The location of the embolism can be reached in surgery;
- 3) Whether or not combined with auto-immune diseases;

Patients were **not eligible** if they had met any one of the following conditions:

- 1) history of other severe diseases and surgical therapy is contraindicated;
- 2) Unwillingness to participate or without informed consent;
- 3) acute pulmonary embolism;
- 4) pulmonary sarcoma;
- 5) Patients with mitral valve diseases, or other conditions that may lead to cardiogenic pulmonary hypertension;
- 6) Pulmonary hypertension caused by pulmonary arteritis.

Intervention information:

Precised analyzed CT scanning and pulmonary angiography will be done for the patients in the precise therapy group, and the patients in Group 1 will receive PEA procedure with the guide of precise 3-D imaging techniques (seen in the picture below)

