Sample size estimation was based on a hypothesis that the mean PAP of patients of PTG can be decreased by 8 mmHg more than that of the traditional group. Given the standard deviation of 12 mmHg was expected in the measurement of mean PAP, with a power of 80% and a significance statistically level of 5% on both side, a sample size of 36 of the PTG group was required.

2) Statistical Analysis:

The analysis was based on the principle of “Intention to Treat” (ITT). All randomized patients (regardless of whether they violate the protocol) will be included in the final analysis.

Continuous variables are presented as mean \pm standard deviation, unless otherwise specified. Significant differences were determined with the Mann-Whitney test or independent t-test according to the their distribution, Wilcoxon matched pairs signed rank test or paired t-test for the paired variables. Categorical variables were compared between the 2 groups using the chi-square test or Fisher exact test. Kaplan-Meier method was used to estimate survival, log-rank test was used to evaluate the survival difference between different groups.

The pulmonary occluded severity will be scored using CT scanning and pulmonary angiography for each patients, the scoring result will be compared with the hemodynamic result to investigate their possible correlations using Spearman Correlation Analysis.

All the statistical analysis were performed using SPSS version 22.0. P value less than 0.05 was considered statistically significant.

7 Quality Control

1) Data accuracy:

All the participants in this study are responsible for the data collection process, all the original medical document should be pictured or scanned as the evidence of recorded data; for parameters with possible subjective error, the original imaging or assessment profile should be saved, the parameters estimated by

2) Group coordination

Fuwai hospital was the largest cardiac surgery center in China and also one of the largest center in the world. Up to now, we had established a coordination team of CTEPH in our center, which consist of cardiac surgery department, pulmonary disease center, radiology department, intensive-care unit and ultra-sonic department, nuclear medicine department in our center.

All the imaging data had been evaluated by at least 2 professional staffs in that field, and the CT constructed imaging, pulmonary angiography imaging had been saved for re-assessment in case of possible subjective bias.

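### The unadjusted Spearman analysis can support the CT/angiography score as a measure of severity, but not the surgical-indications half of Objective 2

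*Combined protocol and SAP*

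**What the plan says.** Section 2 (Objectives), item 2, sets the aim for the score: "establish a quantitative scoring method using CT scanning and pulmonary angiography to assess the severity of CTEPH and surgical indications". Severity and indications are thus two separate claims.

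Section 6, 2) Statistical Analysis, has the only analysis that sets the score against haemodynamics: "the scoring result will be compared with the hemodynamic result to investigate their possible correlations using Spearman Correlation Analysis". The general threshold follows: "P value less than 0.05 was considered statistically significant". There is no covariate, no arm term, no cut-off, and no statement of whether the haemodynamic result is the pre-operative value, the post-operative value or the change. Section 3, 2) records right heart catheterisation immediately before and after surgery, so all three are available.

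Section 5 lists change in CT score as a secondary endpoint. That treats the score as an outcome and does not test it as a guide to surgery.

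Section 4 (Eligibility) requires of every patient: "The location of the embolism can be reached in surgery". Under Arm information, both groups undergo PEA.

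**The concern.** The two halves of Objective 2 need different evidence. For severity, it is enough that the score rises with pre-operative pressure. For anything bearing on whom to operate on, the useful question is whether the score tells the surgeon something about the result of PEA that pre-operative pressure does not already tell. An unadjusted correlation does not separate the two.

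The score is built from the severity of pulmonary occlusion, so a link with pre-PEA pressure is expected if it works as a severity measure. Pre-PEA pressure is one of the two terms in the fall, and it may also be correlated with the post-PEA value. A score that merely restates starting pressure can therefore correlate positively with the fall (suggesting more benefit) and with residual pressure (suggesting a worse result). At stake is how a significant rho would be interpreted: it could be cited for the indications claim when it bears only on severity.

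**Working it through.** **1. The plan's own figure.** Section 6 gives no figure for the Spearman analysis, only a sample size for the between-arm comparison. The inputs are a mean PAP that "can be decreased by 8 mmHg more than that of the traditional group", an SD of 12 mmHg ("the standard deviation of 12 mmHg was expected in the measurement of mean PAP"), and the error rates "with a power of 80% and a significance statistically level of 5% on both side".

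n per arm = 2(1.960 + 0.842)² × 12²/8² = 2 × 7.849 × 2.25 = 35.3, rounded up to 36. This matches the plan, and 2 × 36 = 72 is the number available to the correlation.

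**2. What reaches significance at n=72.** Two-sided 5% is assumed, as the SAP does not state sidedness for this test. Critical |rho| = t/√(70 + t²) with t = 1.994, which gives 0.232. Squared, that is about 5% of rank variance.

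**3. The three readings of the haemodynamic result.**

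| Reading | What an unadjusted rho can show |
|---|---|
| Pre-PEA value | Severity only; nothing addresses indications |
| Post-PEA value | Starting pressure and surgical effect mixed |
| Fall (pre minus post) | Contains starting pressure by construction |

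**4. Illustration: a score that adds nothing beyond pre-PEA pressure.** The assumptions below are not in the documents. The score is pre-operative. Pre and post values have equal SDs. The score/baseline correlation is rs and the pre/post correlation is rp. Given the pre value, score and post value are independent.

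- Score with post value: rs × rp.
- Score with fall: the covariance is rs(1 − rp) and the SD of the fall is √(2(1 − rp)), so the correlation is rs√((1 − rp)/2).
- At rs = rp = 0.5 both equal 0.25.
- Over rs and rp from 0.3 to 0.7, the score/fall correlation runs from 0.3 × √0.15 = 0.116 to 0.7 × √0.35 = 0.414. The score/post correlation runs from 0.09 to 0.49.

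Simulated share of trials with p < 0.05, n=72 (36 per arm):

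| Setting | Against fall | Against post-PEA value |
|---|---|---|
| rs = rp = 0.5, no arm effect | about 53% | about 52% |
| rs = rp = 0.5, 8 mmHg arm effect, SD 12 | about 48% | about 48% |
| rs, rp from 0.3 to 0.7 | about 14-94% | about 10-99% |
| rs = 0.1 | 6-10% across both readings | 6-10% across both readings |

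Rank regression of the post-PEA value on score, pre-PEA value and arm finds the score significant in about 5% of trials (4.6% to 6.1% across the 0.3 to 0.7 settings). With both correlations at 0.5 and no arm effect, the unadjusted score is significantly positive against both the fall and the residual pressure in 19% of trials.

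**5. A second model, with the fall unrelated to baseline.** Here the SD of baseline and the within-arm SD of change are both 12 mmHg, with the 8 mmHg arm effect. The score then carries no information on the fall at all. For rs = 0.3, 0.5 and 0.7:

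- against the fall: about 5% throughout;
- against the post-PEA value: 38%, 81%, 99%;
- against the pre-PEA value: 69%, 99%, 100%.

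If rs = 0, every reading stays near 5%. Across this model's settings, partial Spearman given baseline rejects in 4.8% to 6.1%.

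**6. Who is in the data.** Every patient has disease judged reachable, and every patient is to be operated on. This limit needs no assumption: the score cannot be examined in patients judged inoperable or left unoperated, and those are the patients an indication would have to separate.

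**The case against.** The strongest reply is that nothing is wrong with the test. Spearman is valid for the null of no association. In the step 4 model the score does predict the fall, with a true correlation of 0.25 at the central setting, so 53% is power against a real association. That is correct. A reader might infer that the planned test has an inflated false-positive rate, or that it will reject simply because sicker patients start higher. The documents support neither: the size depends on two correlations they do not give, and it nearly vanishes when the score is only weakly related to baseline.

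The plan also speaks only of possible correlations. It does not say that a significant rho validates the score or will select patients, and the analysis is neither a primary nor a secondary endpoint. That stands, and it limits the weight of the point.

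Three further replies have force. A pre-operative score is independent of randomised arm, so leaving arm out adds noise, not bias. Obstruction may raise pre-operative pressure, so baseline may lie on the path from score to result; adjusting then answers a narrower question of added value, which the protocol does not pose. And section 3, 3) classifies segments by surgical reach and degree of occlusion, so the score may hold anatomical information that pressure does not. The documents do not say how that classification enters the score.

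None of this supplies evidence for the indications half. Whichever reading of the haemodynamic result is taken, the planned correlation alone cannot provide it.

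**Conclusion.** The point holds in limited form. The planned correlation suits the severity claim. It cannot show what the score adds to pre-operative pressure in predicting the result of PEA, and enrolment rules out any test of indications in patients not operated on. The mismatch between objective and analysis, and the enrolment limit, follow from the text alone.

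The percentages are illustrative. They rest on assumed correlations, equal SDs and a score with no information beyond baseline. They show how often such a score could appear related to the result, not an error rate of Spearman's test. A reader might go further and say that a score with no information on surgical gain would look validated. That is literally true only if the result is the pre- or post-operative value; for the fall, the accurate phrase is no information beyond baseline pressure.

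This is a minor matter in an exploratory analysis. The randomised comparison, the sample size and the primary endpoint are untouched.

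**What to change.** 1. **Severity.** Define this analysis as Spearman between the pre-operative score and pre-operative catheterisation values, reported as rho with 95% CI.
2. **Result of PEA.** Name the haemodynamic variable and time point. Add an exploratory regression (rank-based if needed) of the post-PEA value on the pre-operative score, with the pre-PEA value as covariate and arm included for precision. Report the score's coefficient with 95% CI as its added value, alongside the unadjusted rho.
3. **Objective 2.** Narrow the surgical-indications wording to the expected haemodynamic result of PEA in operable patients.

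The cost is a change of wording in the objectives and SAP and one more model in SPSS, on data already collected; no new patients or procedures are needed. The downside is that the adjusted analysis speaks only to added value, is less likely to reach significance, and leaves a narrower claim.

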An example of precise therapy process.A,3-D CT constructed images,which can provide the detailed information of each pulmonary segmental shape and their distribution;B,enhanced CT imaging of pulmonary segment,to assess the occluded severity of each pulmonary segment;C:Diagrammatic sketch of pulmonary artery embolism's location,red marked font refer to pulmonary segments with occupying changes;as shown in the picture,the RA4,RA2,RA5 is completely occluded,other affected segment is partially occluded.D.Surgical specimen;the occupying lesions in each pulmonary segment is stripped according to the embolism location identified by high-resolution CT scanning(seen in picture C);E,clearly opened pulmonary segment entrance after precise stripping therapy.

Arm information:All the patients included into this study met the requirements above and randomized into 2 groups:

group 1:precise PEA therapy with the guide of 3-D imaging techniques;

group 2:traditional PEA therapy solely by surgical probe and traditional CT scanning/pulmonary angiography method.

100 cases of randomized group were generated,which consisted of 50 cases of group 1 and 50 cases of group 2, and 100 cases of randomized number was generated paralleled with the randomized group.According to the date of admission of each patients,they are included into the randomized group one by one,any patient met the criteria of the **not eligible** described above will be excluded from this experiment, and all the patients consent to participate in this study will not know their specific group, the chief surgeon can only know the random grouping situation after the patients been admitted into hospital.

5 Outcome measures and time frame

The primary endpoint for assessment of the efficacy was the peri-operative hemodynamic improvement, peri-operative mortality, major complications after surgery, and deaths in the follow-up period.

Secondary endpoint were the measuring values of NT-pro BNP, parameters of MRI, UCG and CPET in the follow-up period, the CT scoring changes from baseline to follow-up period, and WHO function classes in the follow-up period, as well as disease directly associated cost (average cost) in the follow-up period.

6 Statistical Analysis Plan

This is a prospective randomized single-blinded controlled study, the major endpoint is the hemodynamic improvement after the surgeries.

1) Sample Size:

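### The available text does not mask image readers to arm; an arm-masked read of the saved CT scans would be a cheap improvement for the CT score change endpoint

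*Combined protocol and SAP*

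**What the plan says.** Section 4 (Arm information) sets out who knows the allocation. For patients, "all the patients consent to participate in this study will not know their specific group". For the operator, "the chief surgeon can only know the random grouping situation after the patients been admitted into hospital". No other party is described as masked in the available text.

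Section 7 gives the safeguards for image reading. Under 2) Group coordination, the first safeguard is double reading: "All the imaging data had been evaluated by at least 2 professional staffs in that field". The second safeguard there is an archive: "the CT constructed imaging, pulmonary angiography imaging had been saved for re-assessment in case of possible subjective bias". Under 1) Data accuracy, "for parameters with possible subjective error, the original imaging or assessment profile should be saved". The sentence containing that last phrase then breaks off before it says who estimates these parameters or how.

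Section 5 lists the change in CT score from baseline to follow-up among the secondary endpoints. Section 6, 2) has occlusion severity scored from CT and angiography in every patient. Section 2, item 2) makes the scoring method itself an aim of the study: "establish a quantitative scoring method using CT scanning and pulmonary angiography to assess the severity of CTEPH and surgical indications".

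The imaging work differs by arm. In section 4 the precise analysis of CT and angiography is specified for group 1, and one step of its worked example is "enhanced CT imaging of pulmonary segment,to assess the occluded severity of each pulmonary segment". Group 2 receives "traditional PEA therapy solely by surgical probe and traditional CT scanning/pulmonary angiography method".

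**The concern.** The plan recognises that image reading can be subjective. Its stated answer is a second reader and an archive that may be consulted. A second reader reduces random reading error but does not remove a lean that both readers share because both know the arm. The archived images are kept in case a problem is suspected, and no re-read is scheduled. Masking patients does not protect a score that someone else assigns.

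Among the imaging endpoints, CT score change is probably the most exposed, for two reasons. Its scoring rules are being developed within the trial, so readers have no fixed external standard. It also uses the modality whose analysis differs between arms, so a 3-D reconstruction on the screen could reveal group 1.

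At stake is the reading of one secondary endpoint. If readers know the arm and read one time point differently by arm, part of any difference in CT score change would reflect the reading and not the lesion removed.

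**Working it through.** **1. The plan's own figure.** Section 6, 1) gives a difference of 8 mmHg, SD 12 mmHg, 80% power and two-sided 5%. Then n per arm = 2 × (1.960 + 0.842)² × 12² / 8² = 2 × 7.849 × 2.25 = 35.3, rounded up to 36, or 72 in total. The stated 36 and 72 reproduce. They rest on mean PAP, which is not an image read.

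**2. Which reading errors matter.** Let the mean reading error be a_B and a_F at baseline and follow-up in group 1, and b_B and b_F in group 2. The bias in the between-arm difference in change is

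(a_F − a_B) − (b_F − b_B).

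An over-read common to both arms at a given time point drops out. So does an over-read in one arm that is equal at both time points. Only an error that differs by both arm and time point remains.

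**3. Illustrative size.** The documents give no SD or reader error for the CT score, so every lean below is an assumption, in SD of the change score. With no true effect and a two-sided 5% t-test, the noncentrality is lean / √(2/n), and the false-positive rate is the probability that the noncentral t exceeds the critical value in either direction. √(2/36) = 0.236 and √(2/25) = 0.283. The 25 per arm is an assumed number with usable scans.

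| Net lean (assumed) | 36 per arm (70 df): ncp, rate | 25 per arm (48 df): ncp, rate |
|---|---|---|
| 0 | 0, 5.0% | 0, 5.0% |
| 0.05 SD | 0.212, 5.5% | 0.177, 5.3% |
| 0.10 SD | 0.424, 7.0% | 0.354, 6.4% |
| 0.24 SD | 1.018, 17.1% | 0.849, 13.2% |

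The plan also allows a Mann-Whitney test. For normal data at 36 per arm, simulation gives 6.6% at 0.10 SD and 16.8% at 0.24 SD, which is close to the t-test.

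**4. Check of the cancellation.** In a simulation of change scores (40,000 runs, baseline to follow-up correlation of 0.5 assumed, SD of change 1), an over-read of 0.24 in one arm at both time points leaves the false-positive rate at about 5% for 36 and for 25 per arm. The same over-read at baseline only gives about 17% to 18% at 36 per arm and about 13% at 25.

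**5. What a second reader does.** Suppose reader noise is 20% of the single-read variance (assumption). Averaging two readers reduces the variance from 1 to 0.8 + 0.2/2 = 0.9 and leaves a shared lean unchanged. At 36 per arm, a shared differential lean of 0.2 SD then goes from 13.3% to 14.3% false positives, and 0.3 SD from 24.1% to 26.3%. Double reading does not replace masking.

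**6. Workload of the fix.** 72 patients × 2 readers × 2 time points = 288 CT reads, assuming one follow-up scan per patient.

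**The case against.** The strongest objection is that the gap may lie in lost text. The sentence on subjective parameters in section 7, 1) stops where a rule on readers could stand, and the research-process figure is not shown. This stands as a limit on wording: the finding is that masking is not stated in the available text. A reader might infer that the readers are known to be unmasked, and the documents do not support that.

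A second objection concerns ranking. It would be tempting to call CT score change the most exposed of all secondary endpoints. The documents do not support that either. WHO class is also clinician-rated, with no assessor, masking or second rater stated, and it cannot be re-read from stored images. The narrower claim, probably the most exposed imaging endpoint, is a judgement.

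Third, a reader might infer that the group 1 surgical map doubles as the baseline score. Nothing says so. Section 3, 3) describes CT assessment of segment severity as a general method, apart from the arm-specific text in section 4, which points towards one assessment for both arms. It does not settle the matter, so a sentence separating the two is worth adding as a precaution.

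Fourth, the leans are not estimates for this trial. The 0.24 SD case was chosen as about one standard error of the arm difference, and a lean of exactly one standard error gives about 17% at either sample size. The smaller leans give 5.3% to 7.0%. This objection stands in full: the table shows how sensitive the test is and says nothing about the likely size of the bias.

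Finally, the cost depends on what was kept. The text names constructed CT images as saved. It does not say that source data allowing the same reconstruction are kept for group 2.

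**Conclusion.** The point holds as a proportionate improvement to one secondary endpoint. The stated safeguards for image reads are at least two readers and an archive for re-assessment if needed. Neither removes a lean shared by readers who know the arm, and the available text does not mask them. The bias arises only if the lean differs by both arm and time point. Its direction and size are unknown. Under assumed leans of 0.05 to 0.24 SD with 36 scored per arm, the false-positive rate lies between 5.5% and 17%.

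The mean PAP comparison, deaths and the sample size are not affected. It would go beyond the documents to read this as evidence that the CT results are biased or that the main comparison is compromised. Confidence is medium, mainly because of the cut-off sentence.

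**What to change.** In sections 5 and 7, 2), define the CT score change endpoint as follows:

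- a read of the saved baseline CT and of one pre-specified follow-up CT for each patient;
- by two of the existing readers, masked to arm, and to time point where feasible;
- in the same image format or reconstruction in both arms, where source data are kept;
- with the two readers' scores averaged;
- not taken from the group 1 guidance map.

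Report by arm how many patients lack usable images. Pre-operative assessment and the surgical use of imaging stay as they are in both groups.

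No new scans, patients or readers are needed. The cost is about 288 reads plus image coding and reconstruction, and the scores become available later. Masking of time point will be incomplete, because post-operative anatomy may show. The re-read also cannot correct any difference in how the images were acquired in the two arms.

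If the cut-off sentence in section 7, 1) already masks readers to arm, only the common image format and the separation from the guidance map need to be added.
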